7.4.3 Dose

In order to effectively measure the dose of treatment provided for each participant, we will measure both the dose that was delivered to each person (minutes of each treatment session and number of session) as well as the dose received (recommendations implemented/total recommendations). We will use a spreadsheet or Time Log to track minutes spent in each treatment session and another spreadsheet or Prescription Log to track the recommendations made and implemented for each participant.

7.4.4 Adherence

Adherence measures the participant's continued use of the implemented modifications. We will calculate adherence using the standardized approach that Cumming, et al^[37] used: adherence = recommendations used/total recommendations. Interventionists will rate adherence with intervention at the final session by using the Prescription Log to track recommendations made, implemented and reasons that any recommendations were not implemented. Initial adherence will be a proportion of the number of recommendations implemented /recommendations suggested. Finally, we will determine the number of recommendations used/recommendations suggested at 6 months. Reasons for abandoning strategies will be examined using the Adherence Log; in which the participant will report on current level of use for each modification: very useful, somewhat useful, not at all useful, no longer use equipment. Any independence that was regained by improved sensorimotor performance will not count against the adherence rating.

7.4.5 Safety

To explore the safety of our study, we will measure the number of falls and the circumstances surrounding the falls with a self-report Fall Form used at the 6 month follow up visit. The rate and severity of the falls will be calculated using a standardized algorithm established by Tinetti, et al, 1988^[38]. We will also track both health care utilization for participants in both groups (# of emergency room and out patient visits, # of hospitalizations, and number of days in therapy) using the Health Care Utilization Form.

7.4.6 Cost

The cost of the treatment will be measured by tracking cost of modifications and adaptive equipment for each participant. This will be tracked using the Invoice Form which includes both

costs from the contractor as well as costs of any equipment ordered from a medical supply company or obtained from a community resource (medical equipment lending program). The total amount of money spent on each person will be tracked on this form.

7.5 Overview of study assessments by time point.

	Phone Screening	Consent visit	Baseline assessment	Treatment session (tx group only)	Follow-up months 1-12	5 month phone call (tx group only)	6 month Booster in home (tx group only)	12 month phone call
Consent		x						
Calendar Questionnaire		x						
Demographics		x						
WeHSA			x	x			x	
SMAST-G			x					
GDS		x						
SBT	x							
Medication		x						
ROM			x					
Strength			x					
Grip Strength			x					
Near Visual Acuity			x					
Contrast Sensitivity			x					
POMA			x					
Falls			x	x	x			x
OARS			x					x
FES		x						x
PROMIS		x						x
Falls behavioral Scale		x						x
Fidelity to treatment (visit by visit grid)			x	x			x	
Time (Dose), Completion of Session, Cost				x			x	
Adherence						x	x	x

*randomization before T1

*both groups will send in monthly fall journal information

8 SAFETY ASSESSMENTS

8.1 Safety Parameters

To explore the safety of our study, we will measure the number of falls and the circumstances surrounding the falls and health care utilization for participants in both groups (# of emergency room and outpatient visits, # of hospitalizations, and number of days in therapy) using the Health Care Utilization Form. The rate and severity of the falls will be calculated using a standardized algorithm established by Tinetti, et al, 1988[³⁸]. We will also track both health care utilization for participants in both groups (# of emergency room and outpatient visits, # of hospitalizations, and number of days in therapy) using the Health Care Utilization Form.

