7.3.3.4 Monthly monitoring falls

To record falls, an individually customized calendar journal will be designed for each participant for daily recording of falls^[48]. Our method of tailoring the calendar journal includes life event date anchors, incentives and personalization^[49], we will construct the participant-tailored calendar journals^[50]. There will be space to record the primary outcome of falls (fall or no fall) each day. If a participant falls, they will be instructed to complete a fall form. Calendar journal pages and fall forms will be collected monthly via U.S. mail. Falls will be verified with a follow-up telephone interview by a community coordinator.

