8.2 Adverse Events and Serious Adverse Events

An **adverse event (AE)** are defined as any unfavorable and unintended diagnosis, symptom, sign (including an abnormal laboratory finding), syndrome or disease which either occurs during the study, having been absent at baseline, or if present at baseline, appears to worsen. Adverse events are to be recording regardless of their relationship to the study intervention.

A **serious adverse event (SAE)** is generally defined as any untoward medical occurrence that results in death, is life threatening, requires inpatient hospitalization or prolongation of existing hospitalization, results in persistent or significant disability/incapacity, or is a congenital anomaly.

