8.3 Reporting Procedures

All serious adverse events will be reported to the HRPO in the falling time frames: a) death – immediately; b) life-threatening within 7 calendar days; c) all other SAEs within 15 calendar days using the Electronic Serious Adverse Event Reporting System. Should there be a serious adverse event that occurs that increases the risks to the participants, the study will be stopped, an investigation will be conducted, and a findings report will be generated before the study is resumed.

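### Health care use and adverse events are promised for both arms, but no visible passage schedules their collection, and only the treatment arm has extra contacts, so ascertainment could differ by arm

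*Combined protocol and SAP*

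**What the plan says.** Sections 7.4.5 and 8.1 both promise emergency, outpatient, hospital and therapy use for the two arms: "We will also track both health care utilization for participants in both groups". The instrument is the Health Care Utilization Form. Neither section says when it is given, by whom, or over what recall period.

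Section 8.2 sets a broad recording duty: "Adverse events are to be recording regardless of their relationship to the study intervention". It counts inpatient hospitalization as serious. Section 8.3 adds "All serious adverse events will be reported to the HRPO", with time limits. Neither section says how events are to be elicited.

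Collection is laid out in Section 7.5, "Overview of study assessments by time point". A footnote there says "both groups will send in monthly fall journal information". Section 7.3.3.4 describes the journal: "There will be space to record the primary outcome of falls (fall or no fall) each day". A participant who falls also completes a fall form, and falls are verified by telephone. The treatment sessions, the 5-month call and the 6-month home booster are marked in Section 7.5 as treatment group only.

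**The concern.** A safety measure and a recording duty are stated, but the visible schedule does not collect either. If staff follow Section 7.5 as written, the form is not administered and AEs are learned of incidentally. Incidental learning depends on contact, and scheduled contact differs by arm: a therapist in the home at six months may hear of an admission that no one asks a control about.

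Two things are at stake. Any summary of utilization or AEs by arm could be incomplete and tilted toward more events in the treatment arm. And events unrelated to falls, in either arm, could fail to reach the Human Research Protection Office (HRPO).

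**Working it through.** The plan gives no figure on this point, so the check is mainly a comparison of passages.

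**1. Is there a visible collection point?**

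- Section 7.5 has 22 rows: consent, calendar questionnaire, demographics, baseline clinical measures, falls, the participant-reported scales, fidelity, dose/cost and adherence. None is for the utilization form, health care use, AEs or SAEs.
- At the 12-month call the ticked rows are falls, OARS, FES, PROMIS, falls behavior and adherence.
- Section 7.3.4 (final evaluation) lists the falls behavior scale, OARS, FES-I and PROMIS only.
- Section 7.3.3.5 says follow-up repeats earlier assessments, but none described in Section 7.3.2.3 is a utilization or AE query.
- The monthly journal asks about falls.

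**2. Is scheduled contact equal?** Section 10.3 sets time zero at completion of the intervention.

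| Scheduled contact | Treatment | Control |
|---|---|---|
| Therapist sessions, before time zero | 2 (Section 7.3.3.1) or 2–3 (Section 6.1) | 0 |
| 5-month call | 1 | 0 |
| 6-month home booster | 1 | 0 |
| 12-month call | 1 | 1 |
| Monthly mailed journal | 12 | 12 |
| Verification call after a reported fall | yes | yes |

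Specific live contacts after time zero, leaving out verification calls: treatment 1 + 1 + 1 = 3, control 1, a difference of 2. Over the whole study the treatment count is 5 to 6.

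**3. Do the sections agree about six months?** Section 7.4.5 uses a self-report Fall Form at a 6-month follow-up visit to measure safety. Section 7.2 says controls have no 6-month assessment. Section 7.3.3.4 has fall forms mailed monthly. These need reconciling.

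**4. Direction, and why the size is unknown.** Let p be the true proportion with an event, equal in both arms, and c_T and c_C the fractions captured. The observed ratio is (p × c_T)/(p × c_C) = c_T/c_C. It depends only on the capture fractions, and the documents give none. As an illustration, with every value except the 150 per arm assumed: p from 20% to 40% and c_T = 90%.

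| Assumed c_C | Observed ratio | Chance of two-sided p < 0.05 with no true difference |
|---|---|---|
| 90% | 0.90/0.90 = 1.00 | no bias |
| 70% | 0.90/0.70 = 1.29 | 15% (p = 20%) to 32% (p = 40%) |
| 50% | 0.90/0.50 = 1.80 | 51% (p = 20%) to 87% (p = 40%) |

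The last column uses the normal approximation for two proportions, with pooled variance under the null. For p = 20% and c_C = 70%, the observed proportions are 0.18 and 0.14, with mean 0.16. The null standard error is √(2 × 0.16 × 0.84/150) = 0.0423, and the alternative one is √(0.18 × 0.82/150 + 0.14 × 0.86/150) = 0.0423. Then Φ((0.04 − 1.96 × 0.0423)/0.0423) = Φ(−1.02) = 0.15.

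The table shows how the mechanism works. It does not predict what will happen in this trial.

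**The case against.** Several stronger readings are tempting, and the documents do not support them.

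- **That the plan compares these events between arms.** It says they are tracked and that safety is explored. The only between-arm safety hypothesis (Section 2.1) concerns the fall rate, which has monthly collection in both arms. Section 10.3 plans no test of utilization or AEs. What stands is that safety data collected in both groups are likely to be read by arm.
- **That the form is never given.** The Process Evaluation section refers to Table 1 for data sources, Section 7.1 has a schedule figure, and Section 11.1 points to the MOP. None could be seen, and any of them could set a time point. Section 7.5 calls itself an overview and also omits the fall-verification call. Even so, an overview of assessments by time point should carry a promised safety form.
- **That events will surface mainly in the treatment arm.** This is an inference. No AE query is listed at therapist visits either, and fall-related admissions can surface in both arms through journals, fall forms and verification calls. The exposed gap is mainly events unrelated to falls.
- **That the 39% of controls assumed fall-free (150 × 0.39 = 58.5) have no live contact before month 12.** Section 11.1 mentions telephone data collection at each follow-up point, Section 11.2 allows participant contact to resolve incomplete data, and usual care (Section 6.1) includes an annual in-home evaluation. None of these is an AE query, but they prevent that conclusion.
- **That monthly collection cannot meet the Section 8.3 limits, "b) life-threatening within 7 calendar days; c) all other SAEs within 15 calendar days".** Section 8.3 does not say when the clock starts, so this is at most a point to clarify.

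**Conclusion.** The point holds as a gap in the visible text. Utilization and AE recording are promised, no visible passage gives either a time point or a standard question, and scheduled contact is unequal: three specific live contacts against one after time zero, plus the earlier therapist sessions. Ascertainment of events unrelated to falls could therefore differ by arm, and the likely direction makes the intervention look less safe.

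The size cannot be derived from the documents; under equal capture the bias is nil. The conclusion assumes that Table 1, the Section 7.1 figure and the MOP do not already set a common time point. If one of them does, what remains is to add the row to Section 7.5 and to reconcile Sections 7.4.5 and 7.2. The time-to-first-fall analysis is not affected. This is a cheap improvement to safety data, not a flaw in the primary comparison.

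**What to change.** 1. In Section 7.5, add a row for the Health Care Utilization Form and AE/SAE query, ticked at identical time points in both arms: a short item on the monthly journal page and a scripted question on the existing 12-month call.
2. In Section 8.1, state that any between-arm summary of utilization or AEs uses only these common sources. Events first learned of at therapist contacts are still reported to the HRPO but flagged by source.
3. Reconcile the 6-month visit in Section 7.4.5 with Section 7.2.

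Cost: one table row, a few lines on a page both arms already mail, a few minutes on an existing call, and wording changes. The downside is slightly more participant burden and more SAE reports to process. Events not asked about during follow-up may not be fully recoverable afterwards.

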8.2 Adverse Events and Serious Adverse Events

An **adverse event (AE)** are defined as any unfavorable and unintended diagnosis, symptom, sign (including an abnormal laboratory finding), syndrome or disease which either occurs during the study, having been absent at baseline, or if present at baseline, appears to worsen. Adverse events are to be recording regardless of their relationship to the study intervention.

A **serious adverse event (SAE)** is generally defined as any untoward medical occurrence that results in death, is life threatening, requires inpatient hospitalization or prolongation of existing hospitalization, results in persistent or significant disability/incapacity, or is a congenital anomaly.

8.3 Reporting Procedures

All serious adverse events will be reported to the HRPO in the falling time frames: a) death – immediately; b) life-threatening within 7 calendar days; c) all other SAEs within 15 calendar days using the Electronic Serious Adverse Event Reporting System. Should there be a serious adverse event that occurs that increases the risks to the participants, the study will be stopped, an investigation will be conducted, and a findings report will be generated before the study is resumed.

8.4 Follow-up for Adverse Events

AEs will be followed until resolved or considered stable for the study period.

9 INTERVENTION DISCONTINUATION

Safety data will be collected on any participant discontinued due to an AE or SAE. In any case, every effort must be made to undertake protocol-specified safety follow-up procedures. If voluntary withdrawal occurs, the participant will be asked to continue scheduled evaluations,

complete an end-of-study evaluation, and be given appropriate therapy until the symptoms of any AE resolve or the participant's condition becomes stable.

10 STATISTICAL CONSIDERATIONS

9.1 Sample Size and Randomization

Power computations reflect two general principles. The first is that we will be conservative by underestimating and overstating power. Second, estimates of statistical power will be consistent with the method of analyses. Our primary outcome is time to event; therefore, we will determine the sample size and power within the survival data analyses framework. The Cumming et al.⁷⁹ sample is most similar to our target sample and similar regarding the method of fall ascertainment using daily calendars. On this basis, we assume that approximately 61% of control group participants will fall during 1 year of follow-up. For a meaningful reduction in fall risk, an intervention needs to demonstrate at least 30% reduction in falls.^{105, 106} The Cochrane Review of interventions for preventing falls in older, community-dwelling adults reported that randomized trials of home-safety interventions and personal mobility aids reduced the rate of falls (RaR, 0.59; 95% CI, 0.42–0.82) among high-risk participants defined as having a history of falling or other risk factor for falls.³⁰ Another meta-analysis²⁸ of four randomized trials of environmental interventions, which included some of the same studies as the Cochrane Review, reported a 39% reduction in the risk of falls in high-risk populations, defined as a history of falling in the past year or presence of other risk factors for falling. Because our target sample can be defined as “high risk,” and because our intervention can be defined as a high-intensity home modification, we project a 30% or greater reduction in fall risk at 12 months after treatment. Figure 6 displays the power as a function of total sample size given a fall rate of 42% (event-free rate of 0.58) in the intervention group and a fall rate of 0.61 (event-free rate of 0.39) in the control group, with a 20% attrition rate. A two-sided log-rank test with an overall sample size of 300 participants (150 in each group) achieves 84% power at a 0.05 significance level to detect a difference of 0.19 between 0.39 and 0.58—the proportions without falls in the control and intervention groups, respectively. This corresponds to a hazard ratio of 0.5785 of fall in intervention versus control groups. These results are based on the assumption that the hazard rates are proportional.

10.3 Data Analyses

We will examine the process data before the efficacy analyses.¹⁰⁷ We will use descriptive statistics to describe recruitment rates and reasons for not enrolling. To explore the extent and

[figure not shown]

Figure 6. Power calculation.

quality of the implementation of the intervention, we will compare the characteristics of patients who complete the assigned intervention with those who do not for differences in fall risks. Adherence and cost estimates will be conducted for participants in the intervention group. Descriptive statistics will be used for adherence. We will test the hypothesis that the intervention will have high acceptability (at least 80% retention), high fidelity by therapists (at least 95% of elements and at least 90% of dose delivered), and high adherence to the program (at least 80% of modifications in use) at 12 months. These hypotheses will be tested using a 1-sample 1-sided proportion test. For costs, initial analysis will be conducted to determine what type of approach will be necessary to make unbiased and relevant estimates of the cost of the intervention. We will compare the effectiveness of the program and usual care with the time to the first fall over 12 months as the primary outcome of interest. Survival analysis techniques will be used where time zero is the date on which the intervention is completed, and the ending time is 12 months after the intervention. Participants who do not have a fall will be censored at the end of the study. Participants who move to a nursing home will be censored on the date of moving. For those who fall during follow-up, the time to the first fall will be the event time. Kaplan-Meier product limit estimates will be used to describe the fall experiences for the intervention and control groups, with the log-rank statistic testing for significant difference. Prespecified covariates (e.g., age, race, sex, number of reported medications, mobility, ADL scores, and visual acuity) will be adjusted using the Cox proportional hazards model. We will test the interventions effect using the Cox proportional hazards model and adjusting for covariates. The regression coefficient of the indicator variable quantifies the difference in the log hazard of time to first fall between intervention and control groups. We will determine whether fall-prevention treatment is superior to usual care on secondary outcomes (total number of falls, number of injurious falls) and participant-reported outcomes (daily-activity performance, fall self-efficacy, and global health). We expect that the intervention group will experience fewer total falls, fewer injurious falls, greater daily-activity performance, greater self-efficacy, and greater quality of life compared with the usual care group.

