6 STUDY INTERVENTIONS

6.1 Study Interventions

Control group (usual care). During the treatment phase of the study, each participant randomized to control will receive usual care from SLAAA, which includes annual NAPIS evaluation (in home) and individualized referrals to services based on identified need. Referrals are generated by case managers or SLAAA staff based on the annual assessment or if older adults (or their family members) call and request a referral for services.

Procedures for intervention (treatment). Participants who are randomized to treatment will receive usual care plus the home-modification (home-hazard removal) intervention. The intervention, based on a competence/press theoretical framework,⁹⁶ will be provided by registered and licensed OT. The intervention will be delivered via a manualized intervention using a visit by visit checklist. Home modifications⁷⁹ include a 2-hour home assessment conducted by an OT in the participant’s home using the WeHSA. A comprehensive clinical assessment will be performed on each participant to determine functional limitations that may interact with hazards in the home and result in a fall. Environmental hazards and unsafe behaviors will be identified. A barrier-removal plan will be provided to the older adult. The OT will facilitate home modifications through housing services programs and provided follow-up 2 weeks after the initial home visit to ensure that the participant adopted the recommended modifications. It is anticipated that 2-3 visits of 90 minutes each will be provided. At about 6 months participants will receive a booster session (in home visit by an OT) to reevaluate performance in the home and modify the intervention plan as needed.

Interventionist Training

Each interventionist will receive a 3 hour didactic training and additional 2 hours of guided self-directed learning.

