7.4.2 Fidelity

In order to guarantee treatment fidelity, or our ability to provide the same treatment as planned to each participant, we follow similar methods of Weersing, et al^[36] and use a Visit by Visit Treatment Grid. This grid specifically outlines the pre, during, and post treatment visit requirements for each treatment session. It is designed to be a checklist in which therapists check off the action once it is completed. During weekly interventionist meetings, the lead therapist will review the treatment grid for each participant to guarantee the necessary components of the intervention are being delivered.

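### The unit of analysis for the adherence, fidelity and dose tests is not stated; if items are pooled, the one-sample proportion test ignores clustering, and raw minutes do not fit it

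*Combined protocol and SAP*

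**What the plan says.** Section 10.3 sets benchmarks for retention (80%), for "high fidelity by therapists (at least 95% of elements and at least 90% of dose delivered", and for "high adherence to the program (at least 80% of modifications in use) at 12 months". It then states: "These hypotheses will be tested using a 1-sample 1-sided proportion test". It gives no unit of analysis, alpha or clustering method for these tests. Just before this, the same section says that adherence will be summarised descriptively.

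The data behind the benchmarks are described elsewhere:

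- **Adherence** (section 7.4.4): "adherence = recommendations used/total recommendations". The Process Evaluation section uses the same kind of ratio at 12 months.
- **Fidelity** (section 7.4.2) is read from a visit-by-visit grid: "It is designed to be a checklist in which therapists check off the action once it is completed".
- **Dose delivered** (section 7.4.3) is recorded as "minutes of each treatment session and number of session".
- **Planned dose** (section 6.1): "It is anticipated that 2-3 visits of 90 minutes each will be provided", and "At about 6 months participants will receive a booster session". Section 7.3.3.1 instead gives two visits plus one booster.

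Section 2.1 places these benchmarks under the primary objective.

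**The concern.** A one-sample proportion test needs independent yes/no observations. Retention supplies them. Adherence gives several recommendations per participant, and fidelity gives several checklist actions per participant, delivered by a limited number of therapists. Someone who abandons one modification may well abandon others, so items from one participant are likely to be correlated. If all items go into one binomial count, the standard error is too small and a benchmark is declared exceeded more often than the nominal error allows.

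Dose raises two further questions. Minutes are not a count of successes. The two descriptions of planned visits also leave the denominator of the 90% open.

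At stake is the feasibility claim meant to support dissemination: a programme that only just sits at its benchmark could be reported as having exceeded it.

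**Working it through.** The plan gives no power, sample size or alpha for these tests, so it has no figure of its own to reproduce. Its only stated significance level, 0.05, belongs to the log-rank test.

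**Inputs from the plan.** 150 intervention participants (section 4); 20% attrition (sample size section), so 150 × 0.80 = 120 may give 12-month adherence data; benchmarks of 80% and 95%.

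**Inputs assumed.** One-sided alpha 0.05; true proportion exactly at the benchmark; 3–10 recommendations per participant with intraclass correlation (ICC) 0.05–0.5; 10–30 fidelity elements with ICC 0.05–0.3.

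**Formula for pooled items.** With m items per participant, the design effect is DEFF = 1 + (m − 1) × ICC, and the true one-sided error is about 1 − Φ(1.645/√DEFF). For example, m = 8 and ICC 0.3 give DEFF = 1 + 7 × 0.3 = 3.1, then 1.645/√3.1 = 0.934 and an error of 17.5%. The last column is from a beta-binomial simulation of the pooled z test (40,000 runs for adherence, 30,000 for fidelity).

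| Benchmark | m, ICC | DEFF | Error by formula | Error by simulation |
|---|---|---|---|---|
| Adherence 80% | 3, 0.05 | 1.10 | 5.8% | about 6% |
| Adherence 80% | 8, 0.3 | 3.10 | 17.5% | 17–18% |
| Adherence 80% | 10, 0.5 | 5.50 | 24.2% | about 25% |
| Fidelity 95% | 10, 0.05 | 1.45 | 8.6% | about 9% |
| Fidelity 95% | 30, 0.3 | 9.70 | 29.9% | about 31% |

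An exact binomial test on pooled items gives 4.9–24.7% for adherence and 7.3–30.8% for fidelity. Unequal recommendation counts (2–14 per participant) give 8–25% with the pooled z test.

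**Alternatives, same assumptions.** A participant-clustered test on the logit scale has error of about 5% for adherence and 5–6% for fidelity. A t test on participant proportions has 6–7% and 7–9%.

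**Therapist clustering (fidelity).** The 5–6% holds only if therapists do not differ. With 150 participants, 20 elements and participant ICC 0.1, adding a therapist ICC of 0.01–0.05 (assumed) raises the error of the participant-clustered test to 17–33% with 5 therapists and 12–26% with 10.

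**Participant as unit.** If each participant is classed as reaching 80% or not, the exact test needs 104 of 120 or 129 of 150 and its error is valid for independent participants. The question changes, however: with mean use of 85% over 10 items, only about 77–79% of participants reach 80% (ICC 0.1–0.5). A programme above the stated item-level benchmark would then usually fail.

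**Dose in sessions (illustration).** Two visits plus the booster is 3/3 = 100% under section 7.3.3.1. It is 3/4 = 75% if the possible third visit in section 6.1 counts as planned.

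**The case against.** The strongest reply is that the plan never says items are pooled. Sections 7.4.3 and 7.4.4 log dose, recommendations and adherence for each participant, and a yes/no per participant is a legitimate input to the named test. This stands. A reader might infer that the plan treats correlated items as independent, but the documents do not settle that. The per-item wording of the benchmarks only leans that way, and no participant-level rule for meeting a benchmark is given.

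On dose, a reader might infer that the test is unusable. That is also too strong: sessions delivered out of sessions planned, or participants receiving at least 90% of dose, are proportions. Only raw minutes do not fit. The 75% illustration depends on counting a visit that section 6.1 merely anticipates.

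It is also fair to say that the error rates are driven by assumptions, that section 10.3 may intend adherence to be descriptive only, and that no stopping or decision rule hangs on these benchmarks. The first limits the size of the point. The second does not remove it, because the sentences that follow include adherence among the tested hypotheses. The third bears on priority: time to first fall is the named primary outcome and the only one powered.

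**Conclusion.** The point holds in conditional form. The plan names one test for adherence, fidelity and dose without a unit of analysis. Under the pooled reading that its wording suggests, one-sided 5% error could be about 6–25% for adherence and 9–31% for fidelity. Item counts, ICC and alpha are assumptions; with few items and low ICC the inflation is negligible. Under the participant-level reading the error is valid, but the hypothesis is no longer the stated one. The conclusion on a benchmark can therefore turn on a choice the plan leaves open.

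Two further inferences are not supported. Clustering by participant does not by itself secure the fidelity test, because therapists are a second cluster and the plan does not give their number. Nor does any of this touch the time-to-first-fall analysis. This is a cheap improvement to the feasibility conclusions that the plan should make.

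**What to change.** In section 10.3:

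- **Adherence and fidelity.** Keep the item-level benchmarks and name the item as the unit, clustered by participant. Estimate each pooled proportion by logistic GEE with an independence working correlation, and compare a one-sided 95% lower bound, computed on the logit scale with robust standard errors, with 80% or 95%. A participant-level t test is simpler, with slightly higher error.
- **Fidelity.** Also report results by therapist, and account for therapist clustering where the number of therapists allows. Otherwise state that the bound applies only to the therapists studied. Use an exact or bootstrap method if observed fidelity is 100%, where the logit is undefined.
- **Dose.** Compute each participant's delivered/planned percentage for minutes and for sessions, and report the mean with a one-sided 95% lower bound against 90%. Sections 6.1 and 7.3.3.1 must be reconciled so that the denominator is fixed.
- **Adherence status.** Reconcile the statement that adherence is descriptive with its inclusion in the tests.

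Three items are clarifications only: state the alpha; name the retention denominator (84% passes as 252/300, exact p = 0.046, but not as 126/150, p = 0.129); and cross-refer section 7.4.4, which gives a 6-month ratio, to the 12-month definition in the Process Evaluation section.

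The cost is wording and a different calculation on data already in the treatment grid and logs. The downside is power. With true adherence 85%, 8 items and ICC 0.3, it is about 81% instead of 95–96% with 150 participants, and about 72% instead of 92% with 120. Much of the power given up came from treating correlated items as independent.
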